FDA	Food and Drug Administration
GCLP	Good Clinical Laboratory Practices
GCP	Good Clinical Practices
Hep A total Ab	Hepatitis A total antibody
HBcAb	Hepatitis B core antibody
HBsAb	Hepatitis B surface antibody
HBsAg	Hepatitis B surface antigen
HCV	Hepatitis C Virus
HIV	Human immunodeficiency virus
INR	International normalized ratio
IoR	Investigator of Record
IRB	Institutional Review Board
ISR	Interim Study Review
mL	Milliliter
MWH	Magee-Womens Hospital
NIH	National Institutes of Health
OHRP	Office of Human Research Protections
OUD	Opioid Use Disorder
PHI	Protected Health Information
PI	Principal Investigator
PK	Pharmacokinetics
PoR	Pharmacist of Record
PPM	Postpartum
PRC	Pregnancy Recovery Center
PTID	Participant identification number
QOL	Quality of life
RNA	Ribonucleic acid
SAE	Serious adverse event
SOF	Sofosbuvir
SOF/VEL FDC	Sofosbuvir/velpatasvir fixed-dose combination
SOP	Standard operating procedure(s)
SSP	Study-specific Procedures
SVR	Sustained virologic response
UPMC	University of Pittsburgh Medical Center
VEL	Velpatasvir

RESEARCH TEAM

Principal Investigator: **[name], Msc**
Department of Obstetrics, Gynecology, Reproductive Sciences, Magee-Womens Hospital
[name]
Pittsburgh PA 15213
[contact]
Email: [contact]

Co-investigator: **[name]**
Thomas E. Starzl Transplantation Institute, UPMC Montefiore N758
[name]
Pittsburgh , PA 15213
[contact]
Email: [contact]

Co-investigator: **[name]**
Department of Pediatrics
Children's Hospital of Pittsburgh, [name]
Pittsburgh PA 15213
[contact]
Email: [contact]

Co-investigator: **[name]**
Skaggs School of Pharmacy and Pharmaceutical Sciences, University of Colorado
[name]
Aurora, CO 80045
[contact]
Email: [contact]

Co-investigator: **[name], MSc**
Magee-Womens Hospital of UPMC
[name]
Pittsburgh, PA 15213 USA
[contact]
Email: [contact]

Study Coordinator: **[name]**
Magee Womens Research Institute
[name]
Pittsburgh PA 15213
[contact]
Email: [contact]

SUMMARY

Short Title: Chronic Hepatitis C treatment with Sofosbuvir/Velpatasvir for postpartum women with OUD

Clinical Phase: Phase IV

IND Sponsor:	Exempt
Protocol Chair:	[name], MSc
Sample Size:	30
Study Population:	Postpartum women, a) chronic hepatitis C infection, b) 18 years or older
Study Site:	Magee-Womens Hospital of UPMC, Pittsburgh, PA
Study Design:	Single-site, single-arm prospective study
Study Duration:	2.5 years: 1 year for planned accrual + 1.5 year for postpartum follow-up
Study Medication:	Fixed-dose combination tablet of 400 mg of Sofosbuvir and 100 mg of Velpatasvir (SOF/VEL)
Study Regimen:	Participants will take SOF/VEL one tablet once daily starting within their first 12 months postpartum for 12 weeks total.

Primary Objective:

- Evaluate the feasibility/acceptability of a combined, peripartum HCV and opioid maintenance treatment clinical protocol on adherence to HCV treatment regimens

Primary Endpoint:

- Treatment feasibility will be established through the successful recruitment and enrollment of participants, administration of sofosbuvir/velpatasvir in the postpartum period and ability to determine SVR at 3 months following treatment completion.
- Acceptability of sofosbuvir/velpatasvir will be evaluated by self-report of treatment side effects and barriers and facilitators to treatment adherence.
- Adherence to sofosbuvir/velpatasvir will be evaluated with medication diaries, an assessment of missed doses, pill counts and attendance at opioid maintenance treatment visits.

Secondary Objectives:

- To investigate SOF/VEL drug levels in breast milk.
- Evaluate the rate of IVDU recidivism, HCV reinfection and health related QOL in women with OUD during the first postpartum year.

Secondary Endpoints:

- Breast milk concentrations of SOF, the SOF metabolite GS-331007 and VEL
- Rates of IVDU recidivism
- HCV reinfection
- Patient centered outcomes such as health related QOL will be assessed at 6, 9 and 12 months following treatment completion

Table 1: Study Visit Schedule

	Study Visit	Time Period*
V1	Screening A	6 weeks 0 days to 12 months PPM
V2	Screening B	6 weeks 0 days to 12 months PPM

V3	Enrollment	6 weeks 0 days to 12 months PPM
V4**	Treatment initiation	1 day PPM – 12 months PPM
VPK1-5***	Breastmilk PK visits	2-10 days PPM
V5	2 week treatment follow-up	14 days after treatment initiation
V6	4 week treatment follow up	28 days after treatment initiation
V7	6 week treatment follow-up	42 days after treatment initiation
V8	8 week treatment follow-up	56 days after treatment initiation
V9	10 week treatment follow-up	70 days after treatment initiation
V10	End of Treatment Visit 12 weeks treatment follow-up	84 days after treatment initiation
V11	SVR Visit 3 months post-treatment follow-up	6 months after treatment initiation
V12	9 months post-treatment follow-up	12 months after treatment initiation
V13	End of Study 15 months post-treatment follow up	18 months after treatment initiation

*These are target windows. If the participant cannot be seen within these windows then it will not be considered a protocol deviation

**Start SOF/VEL and continue for 12 weeks

***For a subset of participants, n=5

KEY ROLES

Protocol Identification

Protocol Title: Management of HCV infection in pregnant and postpartum women with OUD: the potential of an integrated medical home model

Short Title: Chronic Hepatitis C treatment with Sofosbuvir/Velpatasvir for postpartum women with OUD

Date: May 10, 2017

Funders, Sponsor and Monitor Identification

Funding Agency: Gilead Sciences Investigator Initiated Studies Program

Site Monitoring: [name] MSc

Pharmaceutical Collaborator: Gilead Sciences

INTRODUCTION

Background

Intravenous drug use (IVDU) is the leading cause of new Hepatitis C virus (HCV) infections and is widespread among pregnant women with OUD. HCV screening during pregnancy is recommended for women with risk factors for HCV exposure and provides a unique opportunity to identify the virus among high-risk women of reproductive age. HCV positivity in pregnant women with OUD ranges from 40-75% and over 28% are newly diagnosed with HCV during pregnancy. Pregnancy is a unique opportunity to engage HCV-infected women in efforts to improve their health and facilitate HCV treatment. However, less than 2% of HCV-infected pregnant patients initiate HCV treatment within one year following delivery.

Rationale

Incorporating HCV treatment into opioid maintenance treatment program clinical protocols is an innovative health care delivery model that has been associated with improved HCV treatment uptake in non-pregnant, drug-using populations. This “medical home” approach would combine HCV and opioid maintenance treatment into one treatment regimen and incorporate the expertise of obstetricians, hepatologists, substance abuse treatment providers and pediatricians into one comprehensive clinical care model. We hypothesize that co-locating prenatal care, HCV treatment and substance abuse treatment services in the same clinical environment will significantly improve HCV treatment uptake and compliance as well as facilitate ongoing recovery from opioid addiction.

SOF/VEL Fixed Dose Combination

Description

The study medication is a fixed-dose combination tablet containing sofosbuvir and velpatasvir for oral administration. Sofosbuvir is a nucleotide analog HCV NS5B polymerase inhibitor and velpatasvir is an NS5A inhibitor.

Each tablet contains 400 mg sofosbuvir and 100 mg velpatasvir. The tablets include the following inactive ingredients: copovidone, croscarmellose sodium, magnesium stearate, and microcrystalline cellulose. The tablets are film-coated with a coating material containing the following inactive ingredients: iron oxide red, polyethylene glycol, polyvinyl alcohol, talc, and titanium dioxide.

Sofosbuvir: The IUPAC name for sofosbuvir is (S)-Isopropyl 2-((S)-(((2R,3R,4R,5R)-5-(2,4-dioxo-3,4-dihydropyrimidin-1(2H)-yl)-4-fluoro-3-hydroxy-4-methyltetrahydrofuran-2-yl)methoxy)-(phenoxy)phosphorylamino)propanoate. It has a molecular formula of C₂₂H₂₉FN₃O₉P and a molecular weight of 529.45. Sofosbuvir is a white to off-white crystalline solid with a solubility of at least 2 mg/mL across the pH range of 2–7.7 at 37 °C and is slightly soluble in water.

Velpatasvir: The IUPAC name for velpatasvir is Methyl {(1R)-2-[(2S,4S)-2-(5-{2-[(2S,5S)-1-[(2S)-2-[(methoxycarbonyl)amino]-3-methylbutanoyl]-5-methylpyrrolidin-2-yl]-1,11-dihydro[2]benzopyrano[4',3':6,7]naphtho[1,2-d]imidazol-9-yl]-1H-imidazol-2-yl)-4-(methoxymethyl)pyrrolidin-1-yl]-2-oxo-1-phenylethyl}carbamate. It has a molecular formula of C₄₉H₅₄N₈O₈ and a molecular weight of 883.0. Velpatasvir is practically insoluble (less than 0.1 mg/mL) above pH 5, slightly soluble (3.6 mg/mL) at pH 2, and soluble (greater than 36 mg/mL) at pH 1.2.

Mechanism of Action

Sofosbuvir is an inhibitor of the HCV NS5B RNA-dependent RNA polymerase, which is required for viral replication. Sofosbuvir is a nucleotide prodrug that undergoes intracellular metabolism to form the pharmacologically active uridine analog triphosphate (GS-461203), which can be incorporated into HCV RNA by the NS5B polymerase and acts as a chain terminator. In a biochemical assay, GS-461203 inhibited the polymerase activity of the recombinant NS5B from HCV genotype 1b, 2a, 3a, and 4a with an IC₅₀ value ranging from 0.36 to 3.3 micromolar. GS-461203 is neither an inhibitor of human DNA and RNA polymerases nor an inhibitor of mitochondrial RNA polymerase. Sofosbuvir has a very short half-life in plasma. SOF accounts for only ~4% of the drug related material circulating in plasma. The majority (>90%) of the drug-related material in plasma is in the form of GS-331007, an inactive metabolite of sofosbuvir.

Velpatasvir is an inhibitor of the HCV NS5A protein, which is required for viral replication. Resistance selection in cell culture and cross-resistance studies indicate velpatasvir targets NS5A as its mode of action.

Clinical Studies

Clinical Studies of Sofosbuvir/Velpatasvir for the Treatment of HCV

Approximately 1035 participants have been enrolled in several multicenter, Phase 3 trials to assess the efficacy of treatment with SOF/VEL in patients with genotype 1, 2, 3, 4, 5 and 6 chronic hepatitis C virus infection.

Table 2: Study ASTRAL-1: Virologic Outcomes by HCV Genotype in SOF/VEL Treated Subjects without Cirrhosis or with Compensated Cirrhosis (12 Weeks After Treatment)

	EPCLUS 12 Weeks (N=624)							
	Total (all GTs) (N=624)	GT-1			GT-2 (N=104)	GT-4 (N=116)	GT-5 (N=35)	GT-6 (N=41)
		GT-1a (N=210)	GT-1b (N=118)	Total (N=328)				
SVR12	99% (618/624)	98% (206/210)	99% (117/118)	98% (323/328)	100% (104/104)	100% (116/116)	97% (34/35)	100% (41/41)
Outcome for Subjects without SVR								
On-Treatment Virologic Failure	0/624	0/210	0/118	0/328	0/104	0/116	0/35	0/41
Relapse ^a	<1% (2/623)	<1% (1/209)	1% (1/118)	1% (2/327)	0/104	0/116	0/35	0/41
Other ^b	1% (4/624)	1% (3/210)	0/118	1% (3/328)	0/104	0/116	3% (1/35)	0/41

GT = genotype; no subjects in the placebo group achieved SVR12.

- a. The denominator for relapse is the number of subjects with HCV RNA <LLOQ at their last on-treatment assessment
- b. Other includes subjects who did not achieve SVR and did not meet virologic failure criteria.

Table 3: Study ASTRAL-3: Virologic Outcomes in Subjects with Genotype 3 HCV without Cirrhosis or with Compensated Cirrhosis (12 Weeks After Treatment)

	EPCLUS 12 Weeks (N=277)	SOF + RBV 24 Weeks (N=275)
SVR12	95% (264/277)	80% (221/275)
	Treatment difference +14.8%; 95% confidence interval (+9.6% to +20.0%)	
Outcome for subjects without SVR		
On-Treatment Virologic Failure	0/277	<1% (1/275)
Relapse ^a	4% (11/276)	14% (38/272)
Other ^b	1% (2/277)	5% (15/275)

SOF = sofosbuvir; RBV = ribavirin.

- a. The denominator for relapse is the number of subjects with HCV RNA <LLOQ at the last on-treatment assessment
- b. Other includes subjects who did not achieve SVR and did not meet virologic failure criteria.

Safety

The adverse reactions data for SOF/VEL in patients without cirrhosis or with compensated cirrhosis were derived from three Phase 3 clinical trials (ASTRAL-1, ASTRAL-2, and ASTRAL-3) which evaluated a total of 1035 subjects infected with genotype 1, 2, 3, 4, 5, or 6 HCV, without cirrhosis or with compensated cirrhosis, who received SOF/VEL for 12 weeks. SOF/VEL was studied in placebo- and active-controlled trials. The proportion of subjects who permanently discontinued treatment due to adverse events was 0.2% for subjects who received SOF/VEL for 12 weeks. The most common adverse reactions (adverse events assessed as causally related by the investigator and at least 10%) were headache and fatigue in subjects treated with SOF/VEL for 12 weeks.

Adverse reactions, all grades, observed in greater than or equal to 5% of subjects receiving 12 weeks of treatment with SOF/VEL in ASTRAL-1 include headache (22%), fatigue (15%), nausea (9%), asthenia (5%), and insomnia (5%). Of subjects receiving SOF/VEL who experienced these adverse reactions, 79% had an adverse reaction of mild severity (Grade 1). With the exception of asthenia, each of these adverse reactions occurred at a similar frequency or more frequently in subjects treated with placebo compared to subjects treated with SOF/VEL (asthenia: 3% versus 5% for the placebo and SOF/VEL groups, respectively). The adverse reactions observed in subjects treated with SOF/VEL in ASTRAL-2 and ASTRAL-3 were consistent with those observed in ASTRAL-1. Irritability was also observed in greater than or equal to 5% of subjects treated with SOF/VEL in ASTRAL-3.

Rationale for Study Design

Incorporating HCV treatment into opioid maintenance treatment program clinical protocols is an innovative health care delivery model that has been associated with improved HCV treatment uptake in non-pregnant, drug-using populations. This “medical home” approach would combine HCV and opioid maintenance treatment into one treatment regimen and incorporate the expertise of obstetricians, hepatologists, substance abuse treatment providers and pediatricians into one comprehensive clinical care model.

OBJECTIVES

Primary Objective

1. To evaluate the feasibility/acceptability of a combined, peripartum HCV and opioid maintenance treatment program on adherence to HCV treatment regimens.

Secondary Objectives

1. To investigate SOF/VEL drug levels in breast milk.
2. Evaluate the rate of IVDU recidivism, HCV reinfection and health related QOL in women with OUD during the first postpartum year.

STUDY DESIGN

Identification of Study Design

This is a single-site, open label, single-arm Phase IV trial.

Summary of Major Endpoints

Primary Endpoints:

- **Treatment Feasibility**
 - Successful recruitment and enrollment of participants
 - Administration of SOF/VEL in the postpartum period
 - Ability to determine SVR at 3 months following treatment
- **Acceptability**
 - Self-report of treatment side effects
 - Self-report of barriers and facilitators to treatment adherence
- **Adherence**
 - Medication diaries
 - Assessment of missed doses

- Pill counts
- Attendance at opioid maintenance treatment visits

Secondary Endpoints:

- Breast milk concentrations of SOF, GS-331007, and VEL
- Rates of IVDU recidivism
- HCV reinfection
- Patient centered outcomes such as health related QOL will be assessed at 6, 9 and 12 months following treatment completion
- Pregnancy and delivery outcomes collected prospectively by chart review and participant interview

Description of Study Population

The study population will include 30 pregnant and postpartum women between the ages of 18-39 year old (inclusive) at screening who are chronically infected with Hepatitis C virus, as described in Sections 5.2 and 5.3.

Time to Complete Accrual

The approximate time to complete study enrollment is expected to be 12 months.

Expected Duration of Participation

The expected duration for maternal and infant participants is approximately 18 months after SVR Assessment, not including the screening window. Maternal study data will be collected from the participant and/or her medical records through the End of Study Visit (15 month post-treatment visit, V14). Infant study data will be collected from his/her medical record after End of Study Visit (15 month post-treatment visit, V14).

STUDY POPULATION

Selection of the Study Population

The inclusion and exclusion criteria in Sections 5.2 and 5.3 will be utilized to ensure the appropriate selection of study participants.

Recruitment

HCV-infected pregnant or postpartum women will be recruited from the outpatient obstetrical clinics at Magee-Womens Hospital (MWH) of UPMC. There are over 10,000 deliveries at MWH per year and it is estimated that approximately 1% of women who deliver are infected with HCV. Recruitment will be primarily targeted from the MWH Pregnancy Recovery Center, which was established in 2014 to provide concurrent treatment for OUD with prenatal care, which has an estimated retention rate of 90% for weekly opiate substitution and prenatal visits. There are approximately 120 pregnant women with OUD who receive prenatal care at the Pregnancy Recovery Center per year. The prevalence of HCV infection in this Center is approximately 60%. Recruitment materials will be approved by the University of Pittsburgh Institutional Review Board prior to use.

Retention

The importance of retention will be stressed to the participant at each visit as part of protocol adherence counseling. Once a participant is enrolled, the study staff will make every effort to retain the participants in follow-up to minimize possible bias associated with loss-to-follow-up.

Inclusion Criteria

Women must meet all of the following criteria to be eligible for inclusion in the study. Any exclusionary laboratory values can be repeated at a later date within the screening window. If the repeated laboratory values meet inclusion criteria then the participant can be enrolled. If there is concern that the participant's health status has changed between the enrollment visit and the screening visit or if there is concern by the study investigators that the participant might not remain eligible, the screening laboratories can be repeated prior to enrollment.

- 1) Age 18 or older

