The following procedures will occur at the End of Treatment visit. This visit will be scheduled within 7 days of completion of the 12 week course of study medication. The purpose of this visit will be to collect any remaining study medication and to collect and follow up on any adverse events.

Table 10: End of Treatment Visit

End of Treatment Visit (12 week postpartum follow-up, V10)	
Component	Procedures
Administrative and Regulatory	
 • Review/update locator information • Visit Questionnaire • Record/update AEs • Schedule next visit
Behavioral	
 • Collect remaining study medication and medication administration log • Conduct qualitative interview
Clinical	
 • Review/update medical history • Review/update concomitant medications • Consultation with hepatologist (only if HCV virus not cleared at 8w) • Provide test results if available
Laboratory	
 • HCV RNA • CMP, CBC, GGT

SVR Assessment (3 month post-treatment visit, V11)

The following procedures will occur at the 3 month post-treatment visit

Table 11: SVR Assessment (V11)

SVR Assessment (3 month post-treatment visit, V11)	
Component	Procedures
Administrative and Regulatory	
 • Review/update locator information • Visit Questionnaire • Record/update AEs • Schedule next visit • Conduct qualitative interview
Clinical	
 • Review/update medical history • Provide test results if available • Consultation with hepatologist (by phone)
Laboratory	
 • HCV RNA • CMP, CBC, GGT

9 month post-treatment visit (V12)

The following procedures will occur at the 9 month post-treatment visit (V13)

Table 13: 9 month post-treatment visit (V12)

V13: 9 month post-treatment visit	
Component	Procedures
Administrative and Regulatory	
• Review/update locator information• Review infant demographics/sign release(s) for medical records for infant (if necessary)• Schedule next visit
Clinical	
• Review/update medical history• Provide available test results
Laboratory	
• HCV RNA• CMP, CBC, GGT

End of Study Visit (15 month post-treatment visit, V13)

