APPENDIX

APPENDIX I: SCHEDULE OF STUDY VISITS AND EVALUATIONS

	Screening A (V1)	Screening B (V2)	Enrollment (V3)	Treatment Initiation (V4)	Breastmilk PK Visits*	Treatment Follow Up (V5-9)	End of Treatment (V10)	Post treatment (V11)	12 month follow up (V12)	End of Study (V13)
ADMINISTRATIVE AND REGULATORY										
Informed consent(s)	X		X		X					
Assess informed consent comprehension			X							
Sign medical record releases	X			X					X	X
Assignment of PTID			X							
Collect/review locator information	X	X	X	X	X	X	X	X	X	
Visit questionnaire		X				X	X	X		X
Eligibility assessment	X	X								
Eligibility confirmation		X	X	X						
Reimbursement					X					
Record/ update AEs					X	X	X	X	X	X
Schedule next visit	X	X	X	X	X	X	X	X	X	
BEHAVIORAL										
Protocol adherence counseling		X	X	X	X	X	X	X	X	
Contraception counseling					X					
Medication use/adherence counseling					X	X	X	X		***
Qualitative interview							X			X
CLINICAL										
Review medical history and medical records, document findings	X	X	X	X		X	X	X	X	X
Concomitant medications	X	X	X	X		X	X			
Consult with hepatologist		X	X				***	X		
Physical examination (full or modified)		X	X							
Provide available test results			X	X		X	X	X	X	X
Administer timed medication dose					X					
LABORATORY										
Collect breastmilk					X					
Collect Blood		X		X	X	X	X	X	X	
HCV antibody	X**									
HCV RNA viral load	X**					X (V6 or 7)	X	X	X	
HCV Genotype		X**								
HCV Resistance testing							***	***		
HepBsAg	X**									
HepBcAb, HepBsAb		X								
HepA total Ab		X								
HIV	X*									
CBC				X*		X (V6 or 7)	X	X	X	
CMP		X		X*		X (V6 or 7)	X	X	X	
GGT				X		X (V6 or 7)	X	X	X	
PK sampling breastmilk and blood					X					
STUDY MEDICATION										
Provision of Study Medication				X	X	X				
Collect Remaining Study Medication							X			

*For a subset of participants, n=5 **If not collected as part of standard prenatal/postpartum care; can be collected at V2 if within 3 months of treatment initiation ***If clinically indicated

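### None of the three stated quality-of-life timepoints (6, 9 and 12 months after treatment) has a scheduled collection: visits fall at 3, 9 and 15 months, and the 9-month visit lists no questionnaire

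*Combined protocol and SAP*

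**What the plan says.** The QOL endpoint appears in the same words in three places: the Summary (Secondary Endpoints), Study Design (Summary of Major Endpoints) and Statistical Considerations (Secondary Endpoints). It states: "Patient centered outcomes such as health related QOL will be assessed at 6, 9 and 12 months following treatment completion".

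The matching secondary objective, in the Summary and under Objectives, is to "Evaluate the rate of IVDU recidivism, HCV reinfection and health related QOL in women with OUD during the first postpartum year".

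Table 1 puts end of treatment (V10) at "84 days after treatment initiation". Three visits follow:
- V11, the "SVR Visit 3 months post-treatment follow-up", 6 months after initiation
- V12, 9 months post-treatment, 12 months after initiation
- V13, "End of Study 15 months post-treatment follow up", 18 months after initiation

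Table 13 (V12) lists locator update, infant demographics and releases, scheduling, medical history, test results and blood tests. It lists no questionnaire. In Appendix I the row "Visit questionnaire" is marked at V2, V5-9, V10, V11 and V13, and is blank at V12. Table 14 (V13) lists no questionnaire, so it disagrees with Appendix I.

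The Data Analysis section says that QOL will come from validated survey instruments. It names none and assigns none to a visit.

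**The concern.** An endpoint defined by fixed assessment times needs a visit, or another planned contact, at those times, with the instrument listed there. Here two of the three times have no visit, and the third has a visit without a listed questionnaire. Staff who follow the schedule exactly would not produce the endpoint as defined.

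QOL that is not asked at the time cannot be recovered later from records. If the site fills the gap ad hoc, values will be spread over mixed times. With 30 women, few will be comparable at any one time. The objective and the endpoint also describe different periods, so a reader of the results could not tell which question the QOL data answer.

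**Working it through.** **1. Reproduce the plan's visit times.** Inputs from Table 1: V10 at 84 days; V11, V12 and V13 at 6, 12 and 18 months after initiation. With 30.4375 days per month, the course lasts 84 / 30.4375 = 2.76 months.

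| Visit | Months after initiation | Minus 2.76 | Stated in Table 1 |
|---|---|---|---|
| V11 | 6 | 3.24 | 3 |
| V12 | 12 | 9.24 | 9 |
| V13 | 18 | 15.24 | 15 |

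Table 1 is internally consistent. The mismatch lies between Table 1 and the endpoint.

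**2. Compare the endpoint times with the visits.**

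| Stated QOL time after completion | Nearest visit | Distance | Questionnaire listed there? |
|---|---|---|---|
| 6 months | V11 | 2.76 months early | Yes, but not at this time |
| 9 months | V12 | 0.24 month late | No (Table 13 and Appendix I) |
| 12 months | V12 | 2.76 months early (V13 is 3.24 late) | No at V12 |

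Covered: 0 of 3.

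**3. Try other time origins.** The authors may have meant a different starting point.
- From initiation: 6 months is V11, with a questionnaire. 9 months has no visit. 12 months is V12, without a questionnaire. Covered: 1 of 3.
- From delivery, with a start on day 1 to 14 (0.03 to 0.46 month): V11 falls at 6.03 to 6.46 months and V12 at 12.03 to 12.46 months, and no visit is near 9 months. Covered: 1 of 3.

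**4. Compare the endpoint with the objective's period.** Months postpartum = start + 2.76 + QOL time.

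| Start of treatment | 6-month point | 9-month point | 12-month point |
|---|---|---|---|
| Day 1 (0.03) | 8.79 | 11.79 | 14.79 |
| Day 14 (0.46) | 9.22 | 12.22 | 15.22 |
| Month 12 | 20.76 | 23.76 | 26.76 |

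The 12-month point always falls after the first postpartum year, because completion always follows delivery. The 9-month point falls inside that year only for a start within 12 − 9 − 2.76 = 0.24 month, about 7 days. For a start at month 12, V10 to V13 fall at 14.76, 18, 24 and 30 months postpartum, all outside it.

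The start window itself is stated differently across the protocol. Table 1 allows up to 12 months postpartum. The V4 text gives 1-14 days, or up to 12 months if breastfeeding. The Study Endpoints text under Statistical Considerations gives only 1-14 days. These passages need to be reconciled, but the 12-month conflict holds under all of them.

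**5. Injection drug use at V12.** Table 13 lists a medical-history update, and Appendix I marks V12 for review of history and medical records. Drug use therefore has a scheduled source at 9 months and lacks only a structured questionnaire there.

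**The case against.** A reader might infer that the QOL data cannot be collected at all. The documents do not support that. Table 1 calls its times target windows, interim visits may occur at any time, and the record-keeping section foresees tracking how participants are contacted for follow-up assessments. Nor does any section say that the visit questionnaire contains the QOL instrument, so a blank questionnaire cell does not strictly prove that QOL is absent at V12. What stands is narrower: nothing in the plan schedules QOL at any stated time.

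A reader might also infer that drug use loses its 9-month assessment, leaving a year between V11 and V13 without data. That is not supported either. V12 keeps history and record review, Pregnancy Recovery Center records are released to the study, and the qualitative interviews cover transmission risk behaviors. HCV reinfection is unaffected at V12, where HCV RNA is drawn.

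Nor is the first postpartum year empty for an early starter. With a day-14 start, the questionnaires at V5 to V11 all fall within it, V11 at about 6.5 months.

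The missing questionnaire in Table 14 is weaker evidence than that in Table 13: its list ends in an empty bullet, and Appendix I marks the item.

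Finally, this may be a drafting slip. Appendix I labels V12 as the 12-month follow-up, which suggests initiation as the origin. Table numbers also skip from 11 to 13, and the last two visits are still called V13 and V14 in places, which suggests that a visit was dropped. Both are inferences. Neither origin gives more than 1 of 3.

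**Conclusion.** The point holds as an inconsistency between endpoint, objective and schedule. None of the three stated QOL times has a scheduled collection, and at most one would under another time origin. The 12-month time also lies outside the objective's period for every participant.

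This rests on two assumptions: that scheduled QOL collection would appear in the visit tables or Appendix I, and that the Appendix I row is read correctly by column position. Table 13 independently agrees with that reading for V12.

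It should be fixed, but it does not threaten the trial. QOL is a descriptive secondary endpoint in a 30-woman, single-site, single-arm pilot, and no primary endpoint or sample-size statement depends on it.

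**What to change.** - Restate the QOL times on visits that exist: baseline (V2), end of treatment (V10), and 3, 9 and 15 months after completion (V11, V12, V13). Use the same wording in all three places.
- Add a questionnaire to Table 13 and to the V12 column of Appendix I. State that it includes the validated QOL instrument, by name, and the drug-use items. Without that statement, adding the questionnaire would not ensure that QOL is collected.
- Make Table 14 agree with Appendix I on the V13 questionnaire.
- Have the investigators reconcile the objective's first postpartum year with the endpoint's time origin. Which period they want to study is their decision.

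The cost is a wording amendment and one extra questionnaire at V12, where blood is already drawn. V13 may already be conducted by phone or email. Keeping 6 and 12 months instead would require two added contacts.
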